# 9.1.5. Confidentiality

The investigator must ensure that participants anonymity will be strictly maintained and that their identities are protected from unauthorized parties. Only an identification code and any other unique identifier(s) as allowed by local law (such as year of birth) will be recorded on any form or biological sample submitted to Gilead, IRB/IEC, or the laboratory. Laboratory specimens must be labeled in such a way as to protect participant identity while allowing the results to be recorded to the proper participant. Refer to specific laboratory instructions or in accordance with local regulations. Note: The investigator must keep a screening log with details for all participants screened and enrolled in the study, in accordance with the site procedures and regulations. Participant data will be processed in accordance with all applicable regulations.

The investigator agrees that all information received from Gilead, including but not limited to the IB, this protocol, eCRFs, study drug information, and any other study information, remains the sole and exclusive property of Gilead during the conduct of the study and thereafter. This information is not to be disclosed to any third party (except employees or agents directly involved in the conduct of the study or as required by law) without prior written consent from Gilead. The investigator further agrees to take all reasonable precautions to prevent the disclosure by any employee or agent of the investigational site to any third party or otherwise into the public domain.

#### 9.1.6. Study Files and Retention of Records

The investigator must maintain adequate and accurate records to enable the conduct of the study to be fully documented and the study data to be subsequently verified. These documents should be classified into at least the following 2 categories: (1) investigator's study file and (2) participant clinical source documents.

The investigator's study file will contain the protocol/amendments, eCRFs, IRB/IEC, and governmental approval with correspondence, the ICF(s), drug records, staff curriculum vitae and authorization forms, and other appropriate documents and correspondence.

The required source data should include sequential notes containing at least the following information for each participant:

• Participant identification.

- Documentation that participant meets eligibility criteria (ie, medical history, physical examination, and confirmation of diagnosis [to support inclusion and exclusion criteria]).
- Documentation of the reason(s) a consented participant is not enrolled.
- Participation in study (including study number).
- Study discussed and date of informed consent.
- Dates of all visits.
- Documentation that protocol-specific procedures were performed.
- Results of efficacy parameters, as required by the protocol.
- Start and end date (including dose regimen) of study drug, including dates of dispensing and return.
- Record of all AEs and other safety parameters (start and end date; causality and severity) and documentation that adequate medical care has been provided for any AE.
- Concomitant medication (start and end date; dose if relevant; dose changes).
- Date of study completion and reason for early discontinuation if it occurs.

All clinical study documents must be retained by the investigator for at least 2 years or according to local laws, whichever is longer, after the last approval of a marketing application in an ICH region (ie, the US, Europe, or Japan) and until there are no pending or planned marketing applications in an ICH region; or, if no application is filed or if the application is not approved for such indication, for 2 years after the investigation is discontinued and regulatory authorities have been notified. Investigators may be required to retain documents longer if specified by regulatory requirements, by local regulations, or by an agreement with Gilead. The investigator must notify Gilead before destroying any clinical study records.

Should the investigator wish to assign the study records to another party or move them to another location, Gilead must be notified in advance.

If the investigator cannot provide for this archiving requirement at the investigational site for any or all of the documents, special arrangements must be made between the investigator and Gilead to store these records securely away from the site so that they can be returned sealed to the investigator in case of an inspection. When source documents are required for the continued care of the participant, appropriate copies should be made for storage away from the site.

#### 9.1.7. Electronic Case Report Forms

An eCRF casebook will be completed by an authorized study personnel member whose training for this function is completed in the electronic data capture (EDC) system unless otherwise directed. The eCRF casebook will only capture the data required per the protocol schedule of events and procedures, unless collected by a non-EDC vendor system (eg, central laboratory). The Inclusion/Exclusion Criteria and Enrollment eCRFs should be completed only after all data related to eligibility are available. Data entry should be performed in accordance with the eCRF Completion Guidelines provided by the sponsor. Subsequent to data entry, a study monitor may perform source data verification. System-generated or manual queries will be issued in the EDC system as data discrepancies are identified by the study monitor or Gilead personnel who routinely review the data for completeness, correctness, and consistency. The site investigator, site coordinator, or other designee is responsible for responding to the queries in a timely manner, within the system, either by confirming the data as correct or updating the original entry, and providing the reason for the update (eg, data entry error). Original entries as well as any changes to data fields will be stored in the audit trail of the system. Regular oversight by the principal investigator of the data entered into the EDC system is expected to occur on an ongoing basis throughout the study to ensure quality and completeness. At a minimum, before any interim, final, or other time points (as instructed by Gilead), the investigator will apply his/her electronic signature to confirm that the forms have been reviewed and that the entries accurately reflect the information in the source documents. At the conclusion of the study, Gilead will provide the site investigator with a read-only archive copy of the data entered. This archive must be stored in accordance with the records retention requirements outlined in Section 9.1.6.

#### 9.1.8. Investigator Inspections

The investigator will make available all source documents and other records for this study to Gilead's appointed study monitors, to IRB/IEC, or to regulatory authority or health authority inspectors.

#### 9.1.9. Protocol Compliance

The investigator is responsible for ensuring the study is conducted in accordance with the procedures and evaluations described in this protocol.

#### 9.2. Sponsor Responsibilities

#### 9.2.1. Protocol Modifications

Protocol modifications, except those intended to reduce immediate risk to study participants, may be made only by Gilead. The investigator must submit all protocol modifications to the IRB/IEC in accordance with local requirements and receive documented IRB/IEC approval before modifications can be implemented.

#### 9.2.2. Study Reports and Publications

A clinical study report (CSR) will be prepared and provided to the regulatory agency(ies) when applicable and in accordance with local regulatory requirements. Gilead will ensure that the report meets the standards set out in the ICH Guideline for Structure and Content of Clinical Study Reports (E3). Note that an abbreviated report may be prepared in certain cases. For studies with sites in countries following the EU Regulation No. 536/2014, a CSR will be submitted within 1 year (6 months for pediatric studies, in accordance with Regulation [EC] No. 1901/2006) after the global end of study (as defined in Section 3.4.2)

Investigators in this study may communicate, orally present, or publish study data in scientific journals or other scholarly media in accordance with the Gilead clinical trial agreement.

#### 9.3. Joint Investigator/Sponsor Responsibilities

#### 9.3.1. Payment Reporting

Investigators and their study personnel may be asked to provide services performed under this protocol (eg, attendance at investigator meetings). If required under the applicable statutory and regulatory requirements, Gilead will capture and disclose to federal and state agencies any expenses paid or reimbursed for such services, including any clinical study payments, meal and/or travel expenses or reimbursements, consulting fees, and any other transfer of value.

#### 9.3.2. Access to Information for Monitoring

In accordance with regulations and guidelines, the study monitor must have direct access to the investigator's source documentation and any participant records in order to verify the adherence to the protocol and the accuracy of the data recorded in the eCRF. The study monitor is responsible for routine review of the eCRF form at regular intervals throughout the study to verify adherence to the protocol and the completeness, consistency, and accuracy of the data being entered on them. The investigator agrees to cooperate with the study monitor to ensure that any problems detected through any type of monitoring (central, off-site, or on-site monitoring) are resolved.

#### 9.3.3. Access to Information for Auditing or Inspections

Representatives of regulatory authorities or Gilead may conduct inspections or audits of the clinical study. If the investigator is notified of an inspection by a regulatory authority, the investigator agrees to notify the Gilead study monitor immediately. The investigator agrees to provide to representatives of a regulatory agency or Gilead access to records, facilities, and personnel for the effective conduct of any inspection or audit.

#### 9.3.4. Study Discontinuation

Gilead reserves the right to terminate the study at any time, and the investigator has the right to terminate the study at his or her site. Should this be necessary, both parties will arrange discontinuation procedures and notify the participants, appropriate regulatory authority(ies) and IRB/IEC. In terminating the study, Gilead and the investigator will ensure that adequate consideration is given to the protection of the participants' interests.

#### 11.2. Pandemic Risk Assessment and Mitigation Plan

During an ongoing pandemic, potential risks associated with participants being unable to attend study visits have been identified for this study.

These risks can be summarized as follows:

- 1) Study drug supplies to participants and sites:
  - a) Participants may be unable to return to the site for a number of visits to get the study drug, or the site may be unable to accept any participant visits. Without study drugs, the participant would not be able to continue receiving the study drug as planned per protocol.

Mitigation plan: Study drug supplies may be provided to the participant from the site without a clinic visit, once it is confirmed that the participant may safely continue on study drug as determined by the principal investigator. A remote study visit, via phone or video conferencing, must be performed before remote study drug resupply. At the earliest opportunity, the site will schedule in-person participant visits and return to the protocol's regular schedule of assessments. A qualified courier may be utilized to ship the study drug from sites to study participants if permitted by the local ethics committee/institutional review board/regulatory authority as applicable and with sponsor's approval.

b) Shipments of study drug could be delayed because of transportation issues. Without study drug, the participant would not be able to continue receiving the study drug as planned per protocol.

Mitigation plan: The site's study drug inventory should be closely monitored. Site staff should notify the sponsor or delegate if they foresee shortage in study drug inventory or if there is any interruption in local shipping service. The sponsor will continue to monitor inventory at the study drug depot and investigational sites. Manual shipments will be triggered as necessary.

- 2) Participant safety monitoring and follow-up:
  - a) Participants may be unable or unwilling to come to the investigational site for their scheduled study visits as required per protocol.

Mitigation plan: For participants who may be unable or unwilling to visit the investigational site for their scheduled study visits as required per protocol, the principal investigator or qualified delegate will conduct a remote study visit, via phone or video conferencing, to assess the participant within the target visit window date whenever possible. During the remote study visit, the following information at minimum will be reviewed:

- i) Confirm if participant has experienced any AEs/SAEs/special situations (including pregnancy) and follow up on any unresolved AEs/SAEs.
- ii) Review the current list of concomitant medications and document any new concomitant medications.
- iii) If applicable, confirm electronic diary questionnaires and participant-reported outcomes have been completed and transmitted.
- iv) If applicable, confirm the participant's study drug supply is sufficient to last until the next planned visit date. If study drug resupply is needed, it will be provided as described above in (1).
- v) If applicable, remind the participant to maintain current dosing and to keep all dispensed study drug kits for return at the next on-site visit.
- b) Participants may be unable or unwilling to travel to the site for planned assessments (eg, safety blood draws); hence samples may not be sent for central laboratory analyses.

Mitigation plan: Local laboratories or other vendors may be utilized as appropriate to monitor participant safety until the participant can return to the site for their regular follow-up per protocol. Any changes in the party conducting laboratory assessments for the study because of the pandemic will be documented accordingly. Pregnancy testing may be performed using a home urine pregnancy test if local laboratory pregnancy testing is not feasible.

c) Participants may be unable or unwilling to attend the study visit to sign an updated informed consent form version.

Mitigation plan: The site staff will follow their approved consent process and remain in compliance with the local ethics committee/institutional review board and national laws and regulations. Remote consent will be allowed if has been approved by the local ethics committee/institutional review board. The consent process will be documented and confirmed by normal consent procedure at the earliest opportunity.

- 3) Protocol and monitoring compliance:
  - a) Protocol deviations may occur in case scheduled visits cannot be conducted as planned per protocol.

Mitigation plan: If it is not possible to complete a required procedure, an unscheduled visit should be conducted as soon as possible when conditions allow. The situation should be recorded and explained as a protocol deviation. Any missed participant visits or deviation to the protocol because of the pandemic must be reported in the eCRF and described in the clinical study report (CSR). Any remote study visits that are conducted in lieu of clinic visits because of the pandemic will be documented as a protocol deviation related to the pandemic.

 b) Study monitors may be unable to carry out source data review or source data verification, or study drug accountability or assess protocol and Good Clinical Practice compliance. This may lead to delays in source data verification, an increase in protocol deviations, or underreporting of AEs.

Mitigation plan: The study monitor is to remain in close communication with the site to ensure data entry and query resolution. Remote source data verification may be arranged if allowed by local regulation and the Study Monitoring Plan. The study monitor is to reference the Study Monitoring Plan for guidance on how to conduct an off-site monitoring visit. The study staff is to save and document all relevant communication in the study files. The status of sites that cannot accept monitoring visits and/or participants on site, must be tracked centrally and updated on a regular basis.

4) Missing data and data integrity:

There may be an increased amount of missing data because of participants missing visits/assessments. This could have an impact on the analysis and the interpretation of clinical study data.

Mitigation plan: Implications of a pandemic on methodological aspects for the study will be thoroughly assessed and documented, and relevant actions will be taken as appropriate (eg, modification of the statistical analysis plan) and in compliance with regulatory authorities' guidance. Overall, the CSR will describe the impact of the pandemic on the interpretability of study data.

Risks will be assessed continuously, and temporary measures will be implemented to mitigate these risks as part of a mitigation plan, as described above. These measures will be communicated to the relevant stakeholders as appropriate and are intended to provide alternate methods that will ensure the evaluation and assessment of the safety of participants who are enrolled in this study.

Since these potential risks are considered mitigated with the implementation of these measures, the expected benefit-risk assessment of GS-5245 in study participants remains unchanged.

#### 11.3. Pregnancy Precautions, Definition of Childbearing Potential, and Contraceptive Requirements

#### 1) Definitions

#### a. Definition of Childbearing Potential

For the purposes of this study, a participant assigned female at birth is considered of childbearing potential following the initiation of puberty (Tanner stage 2, Tanner staging only required if the participant is believed to be prepubescent) until becoming postmenopausal, or unless the participant is permanently sterile or has medically documented ovarian failure. Permanent sterilization includes hysterectomy, bilateral oophorectomy, or bilateral salpingectomy in a participant assigned female at birth of any age.

Participants assigned female at birth are considered to be in a postmenopausal state when they are at least 54 years of age with cessation of previously occurring menses for at least 12 months without an alternative cause. In addition, participants assigned female at birth younger than 54 years with amenorrhea of at least 12 months also may be considered postmenopausal if their follicle-stimulating hormone level is in the postmenopausal range and they are not using hormonal contraception or hormonal replacement therapy.

#### b. Definition of Fertility in a Participant Assigned Male at Birth

For the purposes of this study, a participant assigned male at birth is considered fertile after the initiation of puberty unless the participant is permanently sterile by bilateral orchidectomy or with medical documentation.

# 2) Contraception Requirements for Participants Assigned Female at Birth and of Childbearing Potential

#### a. Study Drug Effects on Pregnancy and Hormonal Contraception

GS-5245 is contraindicated in pregnancy as a malformative effect is noted in early pregnancy based on nonclinical data. An increased rate of adverse fetal effects, including postimplantation loss and fetal visceral malformations related to the development of the heart, blood vessels, and liver, were noted in rabbits administered GS-5245 250 mg/kg/day. Data from clinical pharmacokinetic interaction studies of GS-5245 have demonstrated that there is no reduction in the clinical efficacy of hormonal contraception. Refer to the latest version of the investigator's brochure for additional information.

#### b. Contraception Requirements for Participants Assigned Female at Birth and of Childbearing Potential

The inclusion of participants assigned female at birth and of childbearing potential requires the use of highly effective contraceptive measures with a failure rate of less than 1% per year. They must have a negative pregnancy test at the screening visit before randomization. A pregnancy test will also be performed at the Day 15 visit.

Duration of required contraception for participants assigned female at birth and of childbearing potential in this clinical study should start from the screening visit until 14 days after the last study dose.

Participants assigned female at birth and of childbearing potential must agree to 1 of the following contraceptive methods:

Complete abstinence from intercourse of reproductive potential. Abstinence is an acceptable method of contraception only when it is in line with the participant's preferred and usual lifestyle.

Or

Consistent and correct use of 1 of the following methods of birth control listed below:

- Hormonal or nonhormonal intrauterine device (IUD).
- Subdermal contraceptive implant.
- Bilateral tubal occlusion (upon medical assessment of surgical success).
- Vasectomy in the partner assigned male at birth (upon medical assessment of surgical success).

Or

Participants assigned female at birth and of childbearing potential who wish to use a hormonally based method must use it in conjunction with a barrier method, preferably a male condom. Hormonal methods are restricted to those associated with the inhibition of ovulation. Hormonally based contraceptives and barrier methods permitted for use in this protocol are as follows:

- Hormonal methods (each method must be used with a barrier method, preferably male condom)
  - Oral contraceptives (either combined or progesterone only)
  - Injectable progesterone
  - Transdermal contraceptive patch
  - Contraceptive vaginal ring
- Barrier methods (each method must be used with a hormonal method)
  - Male condom (with or without spermicide)
  - Female condom (with or without spermicide)

- Diaphragm with spermicide
- Cervical cap with spermicide
- Sponge with spermicide

Inclusion of methods of contraception in this list of permitted methods does not imply that the method is approved in any country or region. Methods should only be used if locally approved.

Participants assigned female at birth and of childbearing potential must also refrain from egg donation and in vitro fertilization during treatment and until the end of contraception requirement.

The above requirements apply only as specified, and not to sexual encounters in which pregnancy is not a possible outcome.

#### 3) Contraception Requirements for Participants Assigned Male at Birth

It is theoretically possible that a relevant systemic concentration of study drug may be achieved in a partner assigned female at birth from exposure to the participant's seminal fluid and pose a potential risk to an embryo/fetus. A participant assigned male at birth with a partner assigned female at birth and of childbearing potential must use highly effective contraceptive measures with a failure rate of less than 1% per year through at least 14 days after last dose of study drug. Please refer to the contraceptive requirements listed above for female participants.

Participants assigned male at birth must also refrain from sperm donation or cryopreservation of germ cells during treatment and until the end of contraception requirement.

The above requirements apply only as specified, and not to sexual encounters in which pregnancy is not a possible outcome.

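### The male contraception rule cites fetal exposure through semen but controls only conception, so nothing in the protocol makes a condom or abstinence mandatory when the partner is already pregnant

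*Protocol*

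**What the plan says.** Appendix 11.3 item 3 starts from an exposure route: it is theoretically possible for drug to reach a partner through "seminal fluid and pose a potential risk to an embryo/fetus". The measure that follows is contraceptive. Where the partner is of childbearing potential, a male participant "must use highly effective contraceptive measures with a failure rate of less than 1% per year through at least 14 days after last dose". For acceptable methods the item points elsewhere: "Please refer to the contraceptive requirements listed above for female participants". It also bars sperm donation and germ-cell cryopreservation, and it ends: "The above requirements apply only as specified, and not to sexual encounters in which pregnancy is not a possible outcome".

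The list it points to (item 2b) accepts an intrauterine device, an implant, tubal occlusion or vasectomy, each on its own. The vasectomy entry reads "Vasectomy in the partner assigned male at birth (upon medical assessment of surgical success". Barriers appear only as a partner to hormonal contraception: "Barrier methods (each method must be used with a hormonal method". There the male condom is preferred, but other barriers qualify. Abstinence is one option among several and is worded for intercourse that could lead to conception.

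Item 2a gives the fetal hazard, from rabbits dosed at 250 mg/kg/day: "An increased rate of adverse fetal effects, including postimplantation loss and fetal visceral malformations". It contraindicates the drug in pregnancy.

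**The concern.** The reason and the control do not match. Exposure through semen does not depend on conception during the study, and it applies most directly to a fetus that already exists. A rule that only prevents conception is sufficient for a partner who is not pregnant, because there is then no embryo to expose. It cannot protect a partner who is pregnant when dosing starts, or who becomes pregnant despite contraception.

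At stake is a possible harm to a third party who has not joined the trial: a man could follow item 3 exactly and leave an existing fetus open to the hazard that the item names. This is a participant-protection matter. It does not touch the primary or secondary endpoints or their analysis.

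**Working it through.** The point is textual, so the check sets the passages side by side for a male participant whose partner is pregnant. The plan gives no figure to reproduce.

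1. **Does the base rule reach her?** It applies to partners of childbearing potential. The definition in Appendix 11.3 item 1a makes no exception for current pregnancy, but it is worded for participants, so its application to a partner is not stated. If she is outside it, no rule applies.

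2. **If she is inside it, does the closing sentence release the couple?** Read literally, yes: a new pregnancy cannot result from intercourse during an existing one, so the encounter falls within the exemption.

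3. **If the exemption is read narrowly, what remains?** The item 2b list. An intrauterine device, implant, tubal occlusion or ovulation-inhibiting hormone is not a practical choice for a pregnant woman. That arguably leaves abstinence or vasectomy. A man with a vasectomy complies with no barrier, and vasectomy does not stop exposure to seminal fluid. Hence deleting the closing sentence alone would not close the gap.

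4. **Does another visible passage fill it?**
   - Section 4.3, exclusion criterion 11, concerns unwillingness to use the birth control that the protocol requires.
   - Section 7.4.2.3 asks for reporting and outcome follow-up of partner pregnancies.
   - Appendix 11.3 item 4 lists unacceptable contraceptive methods.
   - Appendix 11.3 item 5 may cover a partner already pregnant at study start, but for partners it requires only reporting.
   - Appendix 11.4 (South Africa and the United Kingdom) adds nothing on partners.

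   None requires a condom or abstinence with a pregnant partner.

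5. **How long is the period?** Dosing lasts 5 days (protocol Section 3.2) and item 3 adds 14 days: 5 + 14 = 19 days. SAP Section 4.2.1 allows a last dose on Day 6 when only one tablet was taken on Day 1: 6 + 14 = 20 days.

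6. **How strong is the hazard evidence?** It is mixed. The rabbit findings in item 2a came from direct dosing. In the rat fertility study (protocol Section 1.2.1.1.1.1), the no-effect level for embryonic toxicity was the highest female dose, at about 6.7 times the projected therapeutic exposure. Those females were dosed only through Gestation Day 7, and the study covered the period up to implantation, so it does not settle later fetal effects. The documents give no concentration in semen and no partner exposure.

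**The case against.** The strongest reply is that this is an inference from silence while relevant documents are unseen. Item 2a sends the reader to the investigator's brochure, and the consent form is a natural place for an instruction to men with pregnant partners. A reader might infer that such men were left uninstructed, or that the sponsor decided to accept the exposure. The documents support neither. They show only that the visible protocol text contains no such rule.

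A second reply is that the closing sentence is generic (item 2b ends with the same one) and need not have been meant to release men with pregnant partners. If the base rule still applies, abstinence or vasectomy is arguably what is left, so it goes too far to say that every reading leaves a pregnant partner without any precaution. That stands. What survives is narrower: even then, no barrier to semen is mandatory.

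Third, a reader might count the listed methods that lack a barrier and treat the share as the size of the problem. It is not, because those methods are meant for couples avoiding conception, and for them preventing conception is enough.

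Finally, the risk is precautionary: the protocol calls the route theoretical, dosing is short, and enrolment stopped on 06 October 2023 (SAP Section 2.3). These points limit the importance of the gap but do not remove it. The sponsor judged the same theoretical route sufficient to require contraception, and the existing fetus falls under the same reasoning.

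**Conclusion.** The concern holds in limited form. Item 3 names fetal exposure through semen as its reason but requires only contraception. Its closing sentence, read literally, exempts a partner who is already pregnant; read narrowly, the rule can still be met without any barrier to semen. No visible passage makes a condom or abstinence mandatory for an existing pregnancy.

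The size is a period of 19 to 20 days per affected participant. The number of affected partners cannot be derived, because the documents give neither the share of men nor the share with pregnant partners. The size of the risk is unknown, and the documents do not establish that transfer through semen is harmful.

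The conclusion assumes that the unseen consent form and brochure do not alter the protocol rule. If they already carry the instruction, what remains is a mismatch between documents. This is a worthwhile wording correction, with no consequence for the trial's results.

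**What to change.** Insert in Appendix 11.3 item 3, directly before the closing sentence:

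> Participants assigned male at birth whose partner is pregnant, or becomes or may be pregnant, must use a male condom or abstain from intercourse from first dose through at least 14 days after the last dose; the exemption below does not apply to these partners.

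The 14 days is item 3's own period. The sentence limits contact with semen and is separate from the contraceptive list. Including a partner who may be pregnant matters because item 2a places the malformative effect in early pregnancy, when a pregnancy may not yet be confirmed.

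Mirror the sentence in the consent form if it is not already there, and carry it into any later protocol that reuses this appendix; the documents do not show whether one exists. The cost is one sentence and a short added restriction on affected couples, with no extra visits, tests or procedures.
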